2.13 Planned Analyses, Sample Size, and Stopping Rules

The Sponsor will conduct the following analyses corresponding to the study objectives and prepare a clinical study report. Where appropriate, descriptive statistics will be used.

Primary Objective:

1. Workflow feasibility:

For each subject, workflow feasibility will be judged as successful or not based on the following criteria:

Treatment for an individual subject will be deemed NOT feasible if:

- Total treatment time on table is greater than one hour OR
- A delay in study treatment of more than 7 business days from simulation to treatment occurs related to the investigational device (excluding delays due to patient or facility factors not related to the study treatment)

2. Toxicities of treatment:

All toxicities will be tabulated and summarized. Toxicities that are possibly, probably, or definitely related to FLASH radiotherapy will be used for the assessment of toxicity of the FLASH treatment.

Note: A dose-limiting toxicity (DLT) is defined as a Grade ≥ 3 toxicity attributed as possibly, probably, or definitely related to FLASH radiotherapy. The number of DLTs will be monitored through the duration of the study and will be used as a criterion in the Stopping Rules (see section 2.13 for a Stopping Rule related to DLT.)

Secondary Objective:

3. Pain relief:

As discussed above in section 2.8.6 patient reported pain score (overall) at baseline and post-treatment (Day 15, Month 1, Month 2, Month 3, long-term) will be assessed using the Brief Pain Inventory (BPI) short form questionnaire. Patient reported pain score for each treated site will be assessed using the Treated Sites Pain questionnaire.

The BPI short form questionnaire was selected to permit the results of this study to be compared with prior published results using this instrument [10].

Per the methodology of Hartsell, et al. [10]: The worst pain score in the BPI short form will be used to assess treatment response; a complete response will be defined as having no pain at 3 months after radiation therapy; a partial response will be defined as a pain score that is at least two points lower than the initial response; a stable response

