will be defined as a one-point change in pain score in either direction; a progressive response will be defined as a pain score that is at least two points higher than the initial score. The same analysis will be applied to the individual sites treated by FLASH, as assessed by the questionnaire with the four-item subset of the BPI questionnaire.

Per the methodology of Chow et al., flare in bone pain due to radiation will be assessed using the Pain Flare questionnaire administered on Day 1 - Day 11. Pain flare is defined as either of the following: a minimum of a two-point increase in the worst pain score for the treated site without a reduction in analgesic intake; or a 25% or greater increase in analgesic intake based on daily oral morphine equivalence without a reduction in the worst pain score. If the worst pain score before treatment was nine or ten, the criteria for pain flare were met if the follow-up worst pain score was ten and reported as worse than the worst pain before treatment with no decrease in analgesic intake. To distinguish pain flare from progression of pain, the worst pain score and analgesic intake had to return to baseline levels during the 11-day (Day 1 - Day 11) time period. Consistent with the Chow study, we will document use of steroid medication.

Data on use of pain medication will be collected and changes in pain medication use will be evaluated between baseline, during each of the first 10 days after treatment, and follow-up visits (Day 15, Month 1, Month 2, Month 3). The percentage of patients requiring narcotic, non-narcotic analgesics, and no pain medications will be assessed and compared to literature values from prior clinical trials.

Sample Size:

For this feasibility study, a sample size of up to 10 patients will apply.

Stopping Rules:

Triggering of a stopping rule will result in a cessation of enrollment and in a review of the study data by the Cincinnati Cancer and Blood Disease Institute Data Safety Monitoring Board and Study Committee (PI and co-investigators).

The study will be stopped if any of the following occurs:

- 3 subjects experience a dose limiting toxicity (DLT) (see section 2.13 for definition of DLT)
- 3 subjects have time on the treatment table >1 hour
- 3 subjects have a delay in study treatment of more than 7 business days from simulation to treatment related to the investigational device (excluding delays due to patient or facility factors not related to the study treatment.)

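### Read literally, the pain response categories in section 2.13 leave an unchanged score unclassified, place each complete response from a non-zero baseline in two categories, and are never linked to analgesic use

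*Combined protocol and SAP*

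**What the plan says.** Pain relief is the only secondary objective (section 2.4). Its outcome measures in section 2.5 are the pain score, overall and by treated site, and use of pain medication.

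Section 2.13 bases response on one item: "The worst pain score in the BPI short form will be used to assess treatment response". It attributes the method to the cited 8 Gy trial (reference 10) and gives four categories:

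- Complete: "a complete response will be defined as having no pain at 3 months after radiation therapy".
- Partial: "a partial response will be defined as a pain score that is at least two points lower than the initial response".
- Stable: "will be defined as a one-point change in pain score in either direction".
- Progressive: "a progressive response will be defined as a pain score that is at least two points higher than the initial score".

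The categories are also used by site: "The same analysis will be applied to the individual sites treated by FLASH". On the choice of instrument, the section says: "The BPI short form questionnaire was selected to permit the results of this study to be compared with prior published results using this instrument".

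Medication has its own analysis: "changes in pain medication use will be evaluated between baseline, during each of the first 10 days after treatment, and follow-up visits", these visits being Day 15 and Months 1, 2 and 3. The shares of patients on narcotics, on non-narcotics and on no pain medication are also to be set against published values.

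Pain scores are taken on Day 1 before treatment, at Day 15, at Months 1, 2 and 3, and every 2 months after that (sections 2.2.2 and 2.8.5).

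**The concern.** A response classification should place each assessed subject in exactly one category at a stated time. As written, this one does not.

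1. **Gap.** A change of zero from a non-zero baseline is not a one-point change, and it is not two points either way.
2. **Overlap.** A score of 0 at follow-up is complete, but it is also partial or stable whenever the baseline is 1 or more. No order of precedence is given.
3. **Timing.** Three months is attached to complete response only, although several scores per subject will exist.
4. **Analgesics.** Response depends on the score alone. A subject whose score falls from 8 to 6 after an increase in analgesics is a partial responder. Response and medication are summarised side by side and never crossed, so no planned summary shows how many responders were taking more analgesic. The pain flare rule in the same section does combine score with intake.

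At stake are the partial and stable counts, the number left unclassified, and how a response rate can be read. If the choices are left open, they will be made after the scores have been seen.

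**Working it through.** The plan gives no target, power or expected rate for pain response, so there is no figure of its own to reproduce. The check is a logical enumeration.

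**Inputs.** The four definitions come from section 2.13. The scale is assumed to be whole numbers 0-10; the plan does not state the range, but the flare rule treats ten as the top score. All four categories are assumed to be judged at the same 3-month visit. Let b be the baseline score (1 to 10) and f the follow-up score (0 to 10), giving 10 × 11 = 110 pairs.

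**Literal counts.**

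- Complete (f = 0): 10 pairs.
- Partial (b − f ≥ 2): b − 1 pairs for each b from 2 to 10, so 1 + 2 + … + 9 = 45. Of these, 9 have f = 0 and are also complete, leaving 36 partial only.
- Stable (change of exactly one point): 10 downward + 9 upward = 19. One of them (1 to 0) is also complete, leaving 18 stable only.
- Progressive (f − b ≥ 2): 9 − b pairs for each b from 1 to 8, so 8 + 7 + … + 1 = 36.
- Unchanged (f = b): 10 pairs, with no category.

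| Literal result, baseline 1-10 | Pairs |
|---|---|
| No category | 10 |
| Complete and partial | 9 |
| Complete and stable | 1 |
| Partial only | 36 |
| Stable only | 18 |
| Progressive only | 36 |
| Total | 110 |

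So 10 pairs have no category, 10 have two and 90 have one. The complete count is 10 under every reading. Partial is 45 or 36, depending on whether complete responses are counted in it. Stable is 19 as written, 18 without the 1-to-0 pair, and 28 (18 + 10) once unchanged scores are added.

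**Baseline 0.** The inclusion criteria require painful lesions but set no minimum score. Allowing b = 0 adds 11 pairs, each with one category, including 0 to 0, which is literally complete. The totals become 10 with none, 10 with two and 101 with one, out of 121.

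**Softer reading.** If stable means within one point, the gap closes for baselines 1-10, but all 10 overlaps remain.

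**Could the gap arise in 10 subjects?** The share with an unchanged score is not in the documents. For an assumed share p, the chance of at least one such subject is 1 − (1 − p)^10: 40% for p = 5%, 65% for 10%, 89% for 20% and 97% for 30%. With 10 subjects assessed, each one moves a percentage by 10 points.

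**With an explicit order** (complete, partial, progressive, stable, with stable as −1, 0 or +1): 10 + 36 + 36 + 28 = 110, one category each.

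**The case against.** The strongest reply is that any sensible analyst would resolve this correctly. With partial and progressive both starting at two points, within one point is the natural sense of stable. Complete and partial are ordered labels, so the best category would be reported. The 3-month time point opens a single list and can be carried through it. The definitions are also attributed to a cited trial, which may settle all three. Most of this stands, and it is why the point is small. But none of it is written in the plan, and the cited trial is not available here. Whether the plan's wording departs from that trial is therefore not judged.

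On analgesics, the reply is that score-only response was chosen for comparability, that medication use is a named outcome with its own analysis, and that individual listings are easy to read across with up to 10 subjects. The contrast with the flare rule is also limited, since that rule follows a different cited trial and answers a different question. This stands too, except that no planned summary makes the link.

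Three stronger readings are tempting but not supported:

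- That analgesic use goes unanalysed. It is analysed through Month 3; it is only not joined to response.
- That about 9% of subjects (10 of 110) will be unclassified and as many double-counted. Score pairs are not equally likely, and the plan gives no distribution of scores.
- That a committed comparison of response rates with the 8 Gy trial will be distorted. The plan says the instrument was chosen to permit comparison; the only comparison section 2.13 says will be made is of medication percentages.

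**Conclusion.** The point holds as a defect of definition. On the text as written, an unchanged non-zero score has no category, each complete response from a baseline of 1 or more has two, and only complete response has a time point. A two-point fall after an analgesic increase counts as response, and no planned summary shows how often this occurs.

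The pair counts rest on a 0-10 integer scale, a literal reading and a common 3-month assessment. They establish the logic, not a number of subjects; how many subjects will be affected cannot be derived from the documents.

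Severity is minor. The outcome is secondary and descriptive in up to 10 subjects, and no test or stopping rule uses it. The primary objectives are untouched. The effect is confined to how the pain result is counted and read.

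**What to change.** In section 2.13:

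1. Define stable as a change of −1, 0 or +1 from the Day 1 pre-treatment score.
2. Assign one category per subject and per treated site at Month 3, in the order complete (0 from a baseline above 0), partial, progressive, stable.
3. Report baseline scores of 0 and subjects not assessed at Month 3 as separate rows, with the number assessed. The second row matters because eligibility asks only for a life expectancy above 2 months.
4. Keep this score-only result for any comparison with the cited 8 Gy trial.
5. Add one supplementary descriptive table, at subject level only, crossing response with whether analgesic intake rose from Day 1 to Month 3. Show narcotic use (as oral morphine equivalent), non-narcotic use and steroid use. Label any threshold for a rise as an assumption: the plan's 25% figure is defined only for flare over Day 1 to Day 11, and morphine equivalence does not cover non-narcotics.
6. Do not apply the analgesic condition to individual sites. Intake belongs to the patient, who may have up to 3 treated sites and other metastases, so a rise caused by one lesion could cancel a real response at another.

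The cost is a few sentences and one table. Medications are already reviewed at each visit, but the daily analgesic dose at Month 3 may have to be added if the case report form, which is not in the documents, does not capture it. The number of responders without a rise in analgesics can only equal or fall below the score-only number.

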2.4 Objectives

Primary Objective:

1. Assess workflow feasibility of FLASH radiotherapy in a clinical setting
2. Assess toxicities of treatment

Secondary Objective:

3. Assess pain relief at the treated site(s)

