2.5 Outcome Measures

The outcome measures corresponding to the study objectives are as follows:

Primary Objective Outcome Measures:

1. Workflow feasibility:

- Patient time on the treatment table
- Delays in study treatment related to the investigational device (excluding delays due to patient or facility factors not related to study treatment)

2. Toxicities of treatment:

- Toxicities that are possibly, probably, or definitely related to FLASH radiotherapy
Toxicities will be classified per CTCAE¹ version 5.0

Secondary Objective Outcome Measures:

3. Pain relief:

- Patient reported pain score overall and specifically for treated sites
- Use of pain medication

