2.7 Study Population (Inclusion/Exclusion Criteria)

Patients with up to 3 painful bone metastasis(-es) in the extremities (limbs, excluding feet, hands, wrists) will be evaluated for this study. Only limb bones will be treated with FLASH (excluding feet, hands, wrists). Other bone metastases (i.e., non-limbs or feet, hands, wrists) may be treated with conventional radiation therapy while the patient is on study. Painful lesions of the limb bones must be treatable with fixed protocol field sizes (see below) for each limb bone lesion, without overlap of radiation fields. Patients should have expected life expectancy >2 months, in the judgement of the investigator. Women of childbearing age must verbally deny being pregnant at the time of consent (pregnancy test will be performed prior to CT simulation as per standard of care at the investigational site).

All inclusion criteria must be met and none of the exclusion criteria may be present for a patient to be eligible for the study. All eligibility criteria will be assessed prior to study enrollment.

¹ Cancer Therapy Evaluation Program (CTEP) home page: <http://ctep.cancer.gov>

Patients on this study may be enrolled in additional investigational studies related to their cancer treatment as long as the investigator believes this study and any other study the patient might be enrolled in would not be in conflict.

Inclusion Criteria:

- Patient age at least 18 years
- Up to 3 painful bone metastasis(-es) in the extremities²
- Bone metastases that can be treated using pre-defined treatment field sizes (7.5 cm x 7.5 cm; 7.5 cm x 10 cm; 7.5 cm x 12 cm; 7.5 cm x 14 cm; 7.5 cm x 16 cm; 7.5 cm x 18 cm; 7.5 cm x 20 cm), without overlap of radiation fields
- Life expectancy of >2 months (in the judgement of the investigator)
- Patients who are able to comply with the protocol
- Provision of signed and dated informed consent form

Exclusion Criteria:

- Prior radiotherapy to the treatment site(s)
- Lesions of the feet, hands, wrists are not eligible treatment sites for FLASH
- More than 3 painful bone metastases of the limbs requiring palliative radiotherapy
- Tumor lysis of >50% of the circumferential bone cortex, or other factors considered to place the subject at significant risk of pathologic fracture
- Patients with bone fractures and/or metal implants in the treatment field³
- Patients who will receive cytotoxic chemotherapy within 1 week prior to or 1 week following their planned radiation treatment⁴

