2.8 Procedure

Study activities consist of the following:

1. Screening, Informed Consent, and Baseline Evaluation
2. CT-based Simulation

² Patients with more than 3 painful bone metastases of the limb bones requiring treatment are more likely to have generalized pain that may confound measurement of pain relief response to treatment

³ Proton range and dosimetry is less certain in the presence of metal.

⁴ Exclusion for concurrent therapies that may affect the tissue response to radiation.

3. Treatment Plan Selection
4. QA
5. FLASH Radiotherapy Delivery
6. Pain Assessment Questionnaires
7. Adverse Event Checks
8. Follow-Up

A detailed description of these activities is provided below. Some of the study activities occur during regular visits the subject will have as part of their oncologic care.

The FLASH radiotherapy delivery shall be performed in accordance with written instructions and training provided for this study by the Sponsor. Clinical site staff with appropriate qualifications will be trained on device usage and clinical study operations.

Sponsor representatives may attend the study procedures, with investigator and patient permission, and record observations.

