2.8.6 Pain Assessment Questionnaires

There are several questionnaires used in this study as described below:

Brief Pain Inventory (BPI) short form questionnaire:

Patient reported pain score (overall) at baseline and post-treatment (Day 15, Month 1, Month 2, Month 3, long-term) will be assessed using the BPI short form questionnaire (see section 2.2.2 Schedule of Activities table).

The BPI short form questionnaire was employed in a prior cooperative-group (Radiation Therapy Oncology Group) prospective, phase III, randomized study evaluating the efficacy of 8 Gy radiation for the treatment of painful bone metastases [10]. Using the BPI short form questionnaire will allow comparison of the current study results to these historical data. This form assesses overall pain response without focus on an individual metastasis.

Treated Sites Pain questionnaire:

Additionally, patient reported pain for each treated site at baseline and post-treatment (Day 15, Month 1, Month 2, Month 3, long-term) will be assessed using a four item subset of the questions from the BPI questionnaire (see section 2.2.2 Schedule of Activities table). This form assesses pain response in each treated site.

Pain Flare questionnaire:

An additional three item questionnaire is required only at baseline and for the first 10 days after treatment to assess radiation treatment related flare in bone pain for each treated site (see section 2.2.2 Schedule of Activities table). The questionnaire uses the methodology employed by Chow et al. [12] to specifically identify flare in bone pain. The patient reported questionnaire will be used to collect the following information: for each treated site, worst pain over the last 24 hours and comparison of this worst pain to the worst pain in the treated site on the day of treatment; pain medications usage, including steroid medications.

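### Pain response is scored with no scheduled record of, or rule for, local therapy given after FLASH, and the plan does not say whether the overall or the treated-site score answers objective 3

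*Combined protocol and SAP*

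**What the plan says.** - **Objective and outcome.** Section 2.4 sets the secondary objective as pain relief at the treated site or sites. Section 2.5 lists two scores for it: "Patient reported pain score overall and specifically for treated sites".
- **Response rule.** Section 2.13: "The worst pain score in the BPI short form will be used to assess treatment response". The categories (complete, partial, stable, progressive) depend on the pain score alone, and complete response is read at 3 months. Section 2.13 adds: "The same analysis will be applied to the individual sites treated by FLASH". Neither analysis is named as the main one.
- **Instruments.** Section 2.8.6 says of the BPI short form: "This form assesses overall pain response without focus on an individual metastasis". It says of the Treated Sites Pain questionnaire: "This form assesses pain response in each treated site". Both are given at the same visits. The BPI was chosen so that results could be compared with a published 8 Gy trial.
- **Other radiotherapy.** Section 2.7: "Other bone metastases (i.e., non-limbs or feet, hands, wrists) may be treated with conventional radiation therapy while the patient is on study". No time limit is given.
- **Entry.** Only painful limb metastases are capped, at 3. The footnote to that criterion explains that patients with more are "more likely to have generalized pain that may confound measurement of pain relief response to treatment".

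**The concern.** A response attributed to FLASH should reflect what FLASH did at the site it treated. A score-only rule cannot ensure this once other local therapy intervenes. Suppose a subject's worst pain comes from a spine lesion that is irradiated conventionally in week 2. If that pain settles, the subject can become an overall responder whatever happened in the limb. Conversely, a subject with a fully relieved limb and an untreated painful spine lesion can score as an overall non-responder. If a FLASH site is re-irradiated or operated on before Month 3 and is then pain-free, it scores as a complete response at that site.

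The plan's own footnote recognises that pain elsewhere can confound this endpoint, but the entry cap covers limb lesions only. At stake are the reading of objective 3 and the intended comparison with published 8 Gy results.

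**Working it through.** **1. Which analysis is exposed to which event** (Sections 2.7, 2.8.6 and 2.13 read together)

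| Event after Day 1 | Overall BPI response | Treated-site response |
|---|---|---|
| Conventional radiotherapy to a non-limb, foot, hand or wrist metastasis (permitted) | Relief can count as response | Not directly affected |
| Painful lesion elsewhere, untreated | Limb relief can be hidden | Not directly affected |
| Re-irradiation or surgery at a FLASH site (neither permitted nor prohibited) | Relief can count as response | Relief counts as response |

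The third row is foreseeable. Section 3.1 lists insufficient pain relief and fracture at the metastasis as risks, and Section 2.9 refers fractures to a specialist.

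**2. Whether later therapy is recorded**

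- Section 2.8.1 records earlier cancer treatment at baseline only.
- The schedule (2.2.2), the follow-up lists (2.8.8) and the early-exit list (2.12) draw on pain scores, pain and steroid medication, performance status, physical evaluation and adverse events. None has an item for later radiotherapy or surgery.
- Indirect sources exist: all adverse events are collected (2.8.7), serious events are reported within 24 hours (2.9), and charts are available on request (2.14). None is linked to the pain analysis.

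**3. Size**

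The plan has no figure to reproduce. Its only relevant number is the sample size of up to 10, given without a response rate or power calculation.

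- Subject level: 1/10 = 10 percentage points per misattributed subject.
- Site level: 10 subjects with 1 to 3 sites give 10 to 30 sites, so one misattributed site is 1/30 = 3.3 to 1/10 = 10 points.

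The rest is illustration, with every rate assumed. Let q be the share of subjects given other local therapy by Month 3, with subjects independent.

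- P(at least 1 of 10) = 1 − (1 − q)^10
- P(at least 2 of 10) = 1 − (1 − q)^10 − 10q(1 − q)^9

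| q | At least 1 | At least 2 |
|---|---|---|
| 0.10 | 0.65 | 0.26 |
| 0.20 | 0.89 | 0.62 |
| 0.30 | 0.97 | 0.85 |

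Let p be the true FLASH response rate, and r the chance that later therapy turns a non-responder into an apparent responder. If later therapy is independent of FLASH response, the apparent rate is p + (1 − p)qr.

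- Smallest shift, over p = 0.4 to 0.6, q = 0.1 to 0.3 and r = 0.5 to 0.65: 0.6 + 0.4 × 0.1 × 0.5 = 0.62, or +2 points.
- Largest shift: 0.4 + 0.6 × 0.3 × 0.65 = 0.517, or +11.7 points.

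That is about 0.2 to 1.2 subjects in 10. For scale, exact 95% intervals are 19% to 81% for 5/10 and 26% to 88% for 6/10. The formula covers upward misattribution only; the second row of the first table works the other way.

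**The case against.** The strongest reply is that the plan already contains the right analysis. A site-specific questionnaire is given at the same visits and scored by the same categories, and the permitted radiotherapy does not directly enter it. A reader might infer from the order of Section 2.13 that overall BPI is the only or leading basis for response, so that all relief from radiotherapy elsewhere is credited to FLASH. The documents do not support this: they rank neither analysis. That part of the objection stands. What remains is that the plan does not name the analysis that answers objective 3, and that the site-level analysis is still open to retreatment at the site.

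A reader might also infer that later therapy could never be identified. That goes too far. A fracture would appear as an adverse event, surgery could appear through a serious event report, charts can be requested, and the case report forms are not among the documents. These routes are partial, however. Elective re-irradiation for persistent pain, for example, need not generate an adverse event that names it.

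Entry criteria exclude lesions at significant risk of fracture, and fractures or metal implants in the field, which should limit early surgery. Section 2.12 allows withdrawal when an exclusion criterion is newly met, but this is discretionary and sets no rule for the pain data.

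Finally, counting scores after retreatment as non-response is one choice of estimand among several. The documents do not say how the published 8 Gy trial handled such scores. If it used them as observed, a stricter rule alone would weaken comparability. This is a fair point, and it is why both results should be shown.

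**Conclusion.** The concern holds in limited form. Followed as written, the rule lets the overall response absorb relief from permitted radiotherapy elsewhere or conceal limb relief. It also lets both analyses count relief after retreatment of a FLASH site as FLASH response. Without scheduled data, the analyst cannot reliably correct this later.

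The size is 10 percentage points of overall response per misattributed subject, and 3.3 to 10 points per misattributed site, if 10 subjects are treated. How many would be affected is unknown. A shift from 5/10 to 7/10 would need two such subjects; it is possible arithmetic, not an expectation. The illustrative shifts of 2 to 12 points lie well inside the sampling uncertainty, and the net direction for the overall score is not known.

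A reader might conclude that the historical comparison is uninterpretable. The documents do not show that; they show a comparison with an unrecorded source of bias. Pain response is secondary and descriptive and enters no test, feasibility criterion or stopping rule. The change is worth making because it is cheap, and because the information is hard to recover in full afterwards.

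**What to change.** 1. In Section 2.13, name the Treated Sites worst pain score as the main response measure for objective 3. Keep the overall BPI response as descriptive, for the historical comparison.
2. Add one case report form item at each follow-up visit: any radiotherapy, surgery or other local procedure since the previous visit (counting from Day 1), with type, anatomic site and date.
3. Prespecify that scores at a FLASH site obtained after such therapy at that site do not count as FLASH response. Show the as-observed result alongside, for comparability with the published 8 Gy trial.
4. Flag subjects who had radiotherapy elsewhere during the study in a listing. Separate response rates in subgroups of at most 10 subjects would tell little.

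The cost is one form item, answerable from the visit or chart, and a few sentences of text. There is no added visit or procedure, and no change to clinical management is proposed. The downside is that the stated response rate may be slightly lower.

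### At a pre-treatment worst pain of 10, the score half of the return-to-baseline test cannot fail, so flare is separated from progression by analgesic intake alone

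*Combined protocol and SAP*

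**What the plan says.** All references are to the combined protocol and SAP. Section 2.13 defines pain flare in three steps.

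- **General triggers.** There are two, and one suffices. The first concerns the score: "a minimum of a two-point increase in the worst pain score for the treated site without a reduction in analgesic intake". The second concerns medication: daily intake, converted to oral morphine, is up by at least a quarter while worst pain has not fallen.
- **Trigger near the top of the scale.** "If the worst pain score before treatment was nine or ten", flare is met when "the follow-up worst pain score was ten and reported as worse than the worst pain before treatment with no decrease in analgesic intake".
- **Flare versus progression.** "To distinguish pain flare from progression of pain", the plan states that "the worst pain score and analgesic intake had to return to baseline levels during the 11-day (Day 1 - Day 11) time period".

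Section 2.8.6 describes the Pain Flare questionnaire. For each treated site it records the worst pain over the past day, a "comparison of this worst pain to the worst pain in the treated site on the day of treatment", and use of pain medication. Sections 2.2.2 and 2.8.8 have it completed before treatment and then daily from Day 2 to Day 11.

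**The concern.** The special trigger exists because a number cannot show worsening at the top of the scale, so the subject's own comparison is used instead. The return test goes back to the number and does not mention the comparison. For a site that starts at 10, one diary entry (score 10, worse than before, analgesics unchanged) satisfies the trigger and, on any later day, the return test as well. A site that never improves can therefore carry the label meant for a transient effect.

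What is at stake is the meaning of the flare result at the sites with the most severe pain. The other pain-score rule in 2.13 does not pick these sites up as worse. A progressive response needs a score at least two points above the initial one, which from 10 would be 10 + 2 = 12, off the scale. The daily comparison is the only pain-score information able to register worsening at such a site, and the return test leaves it out.

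**Working it through.** The plan states no flare rate, so there is no figure to reproduce. The check applies the 2.13 rule to defined diary records.

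**Notation.** *b* is the pre-treatment worst pain at the site, *s* the worst pain on a diary day, *c* the comparison with the day of treatment (worse or not), and *a* the analgesic intake divided by baseline intake. Diary days run from Day 2 to Day 11, which is 10 days.

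**Rule as written (section 2.13).**

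- Trigger 1: *s* − *b* ≥ 2 and *a* ≥ 1.
- Trigger 2: *a* ≥ 1.25 and *s* ≥ *b*.
- Trigger 3: *b* is 9 or 10, *s* = 10, *c* = worse, and *a* ≥ 1.
- Return: on a later day up to Day 11, *s* ≤ *b* and *a* ≤ 1.
- Trigger plus return gives flare; trigger without return gives progression.

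Two points are assumptions. The score tops out at 10, which the special trigger implies. One later day at baseline levels is enough, since the text gives no duration.

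**Step 1: the score half at *b* = 10.** Every possible *s* satisfies *s* ≤ 10 = *b*. The return test reduces to *a* ≤ 1.

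**Step 2: a persistent record, *s* = 10 and *c* = worse on all 10 days.**

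| Baseline *b* | Trigger met at *a* = 1.0 | Score half (10 ≤ *b*) | Result, *a* = 1.0 throughout | Result, *a* = 1.25 or 1.5 throughout |
|---|---|---|---|---|
| 7 | 1 (10 − 7 = 3) | fails | progression | progression |
| 8 | 1 (10 − 8 = 2) | fails | progression | progression |
| 9 | 3 | fails | progression | progression |
| 10 | 3 | met | **flare** | progression (intake half fails) |

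**Step 3: other records at *b* = 10, pain still 10 and worse through Day 11.**

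- Intake 1.5 times baseline for 5 days, then back to 1.0: flare.
- Intake 1.0 for the first 2 or 3 days, then 1.5 to Day 11: flare, because Day 2 triggers and Day 3 counts as the return.
- Intake 1.0 on the first day only, then 1.5 to Day 11: progression.

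**Step 4: add the comparison to the return test (*c* not worse on the day of return).** Every record in steps 2 and 3 that came out as flare becomes progression. A transient record at *b* = 10 (worse for 3 days, then 10 and not worse at baseline intake) stays flare. The persistent results at *b* = 7, 8 and 9 do not change. All these records have scores of 10, so the check isolates the comparison item.

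**The case against.** **The intake half still works.** A reader might infer that the ceiling satisfies the whole return test, or that the rule turns flare and progression round. The text does not support that. Both score and intake must return, and a baseline-10 site with raised intake throughout is not flare. The distinction is lost only when intake is at, or comes back to, baseline.

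**Return can be read more strictly.** It may mean that the score must first have left baseline. On that reading a baseline-10 site with unchanged analgesics does not pass; the test is undefined for it. The sentence needs clarifying on either reading.

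**The definition is adopted from a published trial.** The plan takes it from the cited randomised trial of dexamethasone against pain flare, and these documents do not show whether that source settles the ceiling case. This is a good reason to leave the rest of the definition alone. It does not supply the missing rule in the plan's own text.

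**The consequence is limited.** A reader might infer that failed pain relief is being hidden. Response is judged separately, from the BPI and the Treated Sites questionnaire at Day 15, Months 1 to 3 and long term, and the flare label does not enter it. Medication change is evaluated on each of the first 10 days, and all adverse events are collected. Flare feeds no stopping rule. This objection stands.

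**The size is easy to overstate.** If 5% to 20% of sites were assumed to start at 10, the chance of at least one in 10 independent sites would be 1 − 0.95^10 = 40% to 1 − 0.80^10 = 89%. That counts sites that could be affected, not sites misclassified. If a further 5% to 20% of those were assumed to have unresolved worse pain with baseline intake, the range would be 1 − (1 − 0.0025)^10 = 2.5% to 1 − (1 − 0.04)^10 = 34%. None of these shares is in the documents. Nor does the plan specify a per-subject flare proportion, so a shift of 1/10 = 10 points per subject cannot be asserted. Flare is scored per site; with 1 to 3 sites in each of 10 subjects, one site is 1/30 = 3 to 1/10 = 10 points.

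**Conclusion.** The point holds, limited to sites with a pre-treatment worst pain of exactly 10. There the score condition is met automatically, and unresolved worse pain is classed as flare whenever analgesic intake is at or returns to baseline. A baseline of 9 is unaffected, because the score must come back down from 10. This is a stated rule giving a wrong class for a definable set of records, and no other section repairs it.

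The conclusion rests on a scale maximum of 10 and on one later day at baseline levels counting as a return. The reach is small: a descriptive flare analysis under the secondary objective, in up to 10 subjects. No misclassification rate can be stated. It is worth settling before flare data are classified, because the remedy is cheap and the sites concerned have the highest pain scores.

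**What to change.** Add to the flare definition in section 2.13:

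> For a site with pre-treatment worst pain of 10 that met a flare criterion, worst pain has returned to baseline only if, on a later day up to Day 11, it is scored 9 or less, or is scored 10 and not reported as worse than the worst pain before treatment, with analgesic intake at or below baseline. If the completed diary days show no such return, the site is classed as progression; if missing days prevent the assessment, it is reported as not evaluable.

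Keep the rest of the adopted definition. The cost is this short addition and a small change to the derivation program; no new data, visits or subjects are needed. The downside is a slight departure, for this subgroup, from the flare definition as the plan states it. Results under the unmodified wording can be shown alongside.

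The addition does not set how long a return must last. A site that is worse on nine of ten days and not worse on one later day would still be flare. That follows from the absence of a stated duration, which applies at every baseline and is not a ceiling problem.
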